- After receiving LEEP or cryotherapy, women will be given free condoms and advised to abstain from sexual activities for at least 4 weeks. Women will also be offered an information sheet on the treatment procedure and abstinence information to take home for their spouse or partner. Information includes treatment given, recommended abstinence period and reasons for abstaining from sexual intercourse. These information sheets will be optional to maintain patient confidentiality and safety, especially for people who have not disclosed their status.
- Patients undergoing randomization will have the following performed:

- Blood (10mls) will be drawn to check for HIV viral load and CD4 count
 - Cervix will be swabbed to assess the presence of Human Papillomavirus (HPV) prior to LEEP or cryotherapy
 - Cervix will be swabbed for HIV viral level prior to LEEP or cryotherapy
 - LEEP or cryotherapy performed based on randomization envelope
 - Those undergoing LEEP will have the LEEP piece taken for histology
 - “Randomization” questionnaire completed
 - “Treatment” questionnaire completed
4. First, second, and third-week visits for cervical HIV-1 SHEDDING after treatment (~400 patients) (see Study Flow II)
- Patients who have been randomized and received treatment (approximately 400 patients) will be followed every 1 week for 3 weeks AFTER the treatment intervention to assess healing and measure HIV-1 viral shedding from the cervix. These events can be called the 7-9, 8-10, and 9-11-week visit time points and will probably coincide with the eighth, ninth, and tenth week after enrollment. However, for purposes of measuring HIV viral shedding, it is most important that these time points occur 1, 2, and 3 weeks after the treatment intervention. These terms are consistent and are used for descriptive purposes. They will return 3 times over a 3-week interval and have the following performed:
 - Blood (10mls) will be drawn to check for HIV viral load
 - Cervix will be swabbed to assess the presence of HIV-1
 - “Shedding” questionnaire completed

Shedding information will be considered valid if it is obtained \pm 3 days of the scheduled visit. We will collect shedding information for the first three weeks after treatment but if a patient misses those visits but comes back within six weeks, we will still collect the samples just for comparison purposes.

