5. Six, twelve, eighteen, and twenty-four months after randomization visits for RECURRENCE (approximately 400 patients) (see Study Flow II)

- After the 9-11-week visit, randomized participants and those who undergo LEEP but are not randomized because their lesions are not amenable to cryotherapy will return at 6, 12, 18, and 24 months after treatment is administered. At the 24 month visit, the subject will be exited from the study. At these 6-month interval visits, the following will be performed in order:
 - Pap smear to detect recurrence of cervical intraepithelial lesions
 - Same Pap smear swab will be used to assess the presence of Human Papillomavirus (HPV)
 - Blood (5 mls) will be drawn to check for CD4 count
 - “Pap Smear” questionnaire completed
- Pap smear results that are normal, ASCUS, will be filed in the participants file and disclosed at the next scheduled follow-up visit. If pre-cancerous lesions by cytology have recurred then patient will be contacted to return to the study clinic to undergo colposcopic directed biopsy prior to treatment. Results of the colposcopic examination will be entered in the “Colposcopy” questionnaire..
 - If histology-confirmed lesions can be treated by LEEP, then the patient will receive a free LEEP and “Treatment” questionnaire will be filled.
 - If histology-confirmed lesions are too large or cancerous for LEEP then patient will be referred to KNH for subsidized care at this government

hospital. The study will not pay for this treatment. Patients will be given follow-up appointments in the study clinic after referral to determine outcomes.

- Phone calls and home visits will be performed sequentially in the case of a subject who has been lost to follow-up (LTFU) after screening or randomization (see LTFU section). LTFU will be prepared and discussed at weekly clinic meetings. Written reports will be prepared from these meetings and sent to co-investigators. Home visits will be performed by community health workers trained to be discreet in their approach to finding patients. They will not wear clothes that would identify them as health workers and will only use public transportation or unmarked private vehicles. They may ask about the participant's health or whereabouts.

6. Specimen transportation

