3. Will you make audio-visual or tape recordings or photographs of subjects? No Yes. If yes, explain what type of recordings you will make, how long you will keep them, and if anyone other than the members of the research team will be able to see them.
4. Will your study involve use of equipment involving energy input to the subjects (EMG, EKG, MRI, ultrasound, etc.)?
 No Yes. If yes, attach documentation that all equipment will be tested regularly or describe safety testing procedures you will use.

G. REPORTING OF ADVERSE EVENTS

1. Describe how unanticipated adverse events related to study participation will be reported to the local IRB/Ethics Committee.

The IRBs of host institutions and the sponsor, CDC, will be notified of adverse events by the PI within 72 hours of his becoming aware if the adverse events fall into one of two categories:

1. related to research procedures and unexpected and severe

2. related to research procedures and expected, but more severe or occurring at a greater frequency than expected

Severe adverse events related to the study include any death, any non-HIV-related hospitalization, severe infection including PID, severe bleeding or cramping and severe cervical stenosis. Any adverse events will be recorded by study staff on Adverse Events Reporting Forms at the time of the incident or at the next study visit. Documentation of severe adverse events which meet the criteria listed above will be brought to the attention of study PIs within 24 hours by the study doctor and/or study nurse via phone or email, and be assessed.

Other Adverse Events that do not meet the criteria above will be reported to the IRBs as per their specific guidelines.. All serious and non-serious adverse events will be reported to the DSMB during its regular meetings. All Adverse Event reports that are sent to the IRBs and DSMB will also be sent to the study sponsor.

Adverse Events

Specification of Safety Parameters

Safety parameters for this study will include signs and symptoms of local genital irritation and of systemic effects that could be related to either Pap smear screening or study treatment procedures (LEEP or cryotherapy), side effects from any medications prescribed as part of this study, and any other health complications that subjects may experience while enrolled in this study. Methods and Timing for Assessing, Recording, and Analyzing Safety Parameters.

Adverse Events (AEs)

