An AE is any untoward medical occurrence or unintended clinical sign, including an abnormal laboratory finding, symptom or disease, in a clinical investigation subject that occurs during the course of the study. The occurrence is considered an AE whether it is associated with the use of a medical treatment or procedure, or considered unrelated to that medical treatment or procedure. The occurrence of an AE may come to the attention of study personnel in various ways--during study visits, during interviews of a study participant presenting for medical care, or during a review by a study monitor.

All AEs will be:

- recorded on the appropriate AE CRF by the study physician and nurses
- summarized by the data team
- followed through resolution by a study clinician
- reviewed and evaluated by a study clinician
- Study-related SAEs will be immediately reported to the host IRBs and ERCs, and to the study sponsor.

In this study, the following situations will be considered AEs:

1. Occurrences related to Pap smear, LEEP or cryotherapy procedures:

Symptoms such as abdominal pain that lasts longer than 2-3 days, vaginal bleeding and/or discharge, fever, or chills will be assessed at each study visit after obtaining either Pap smear or cervical biopsy.

2. Occurrences related to side effects from prescribed medications related to the study:

If a medication(s) are prescribed for treatment of an infection, subjects will be assessed for any potential side-effects at each visit. These symptoms may include: upset stomach, vomiting or diarrhea, sensitivity to light, rash, severe allergic reaction that could cause death, dizziness, headache, confusion, ringing in the ears or hearing loss, seizures, heart problems, blood disorders, problems with blood sugar, liver disease, kidney disease, and pain or numbness in the arms or legs.

3. New medical problem(s) or worsening of an existing medical problem(s)

Study staff will inquire about any new medical problem or worsening of an existing medical problem since the subject's last visit.

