The meetings will mainly be open sessions. These sessions will be attended by the Principal Investigators or designee. Other research staff may attend the open sessions but this is up to the discretion of the PI. Issues discussed at open sessions will include conduct and

progress of the study, including patient accrual, compliance with protocol, and problems encountered. Patient-specific data and treatment group data will not be presented in these sessions.

Closed sessions may be requested by the DSMB at any time and will be attended by voting DSMB members and the unblinded statistician. Any other trial staff may be requested to attend by the DSMB. All safety and efficacy data will be presented at this session. The discussion at the closed session is completely confidential.

Should the DSMB decide to issue a termination recommendation, the full vote of the DSMB will be required. In the event of a split vote, majority vote will rule and a minority report will be appended. An appeal may be filed by study PIs if a termination decision is made.

Study Stopping Criteria

The DSMB may recommend stopping the study for the following reasons:

- The data show a significantly increased risk of serious adverse effects in one of the treatment arms.
- Interim efficacy analyses show significant treatment benefits or futility in the one treatment group. The interim efficacy analyses are based on pre-specified stopping boundaries for the primary endpoint of the study which preserve the study wide Type I error rate.
- It becomes clear that successful completion of the study is not feasible (e.g. there is an excess of patient dropout, missing data, lack of recruitment etc).

Interim Efficacy Analyses

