1. What is your name?
 - a. First name
 - b. Middle name
 - c. Last name
2. How are you called in your home area?
3. What is the current physical location where you live?
 - a. District
 - b. City
 - c. Village
 - d. Estate
 - e. Plot number
 - f. Door number
 - g. Road name
4. Public Transportation to the house:
 - 4a. Type: F Bus F Boda boda F Matatu F Taxi F Other (specify)
 - 4b. Route number:
 - 4c. Stage Name
 - 4d. General Name of the Area
5. Walking directions to house from the stage?
6. Landmarks that aide in locating the household: (Names of schools, churches, businesses etc.)
7. Can you be reached by phone? Yes No
If yes,
 - 7 (i)What is the phone number 1?
 - 7 (ii)What is the phone number 2?
 - 7iii. Who carries the phone (tick one) self other, specify

B. SIGNIFICANT CONTACT

8. Is there another person who is ware of your HIV status that we can contact through phone if we are unable to reach you directly?
If no, skip to 9.
9. What is the name of this contact person?
a. First name
b. Middle name
c. Last name
10. What is the relationship of this person to you?
11. (a)What is the phone number 1?
(b) What is the phone number 2?

C. UPCOUNTRY INFORMATION

12. Do you have an upcountry home? Yes No
If no, skip to 19
13. What is the physical location of your upcountry home?
a. District
b. City
c. Village
d. Estate
e. Plot number
f. Door number
14. Specific directions to residence
15. Is there person located in your upcountry home whom we can contact if we are unable to reach you directly? Yes No
If no, skip to 19
16. What is the name of this contact person?
a. First name
b. Middle name
c. Last name
17. What is the relationship of this person to you?
18. Does this contact have a phone number? Yes No
If yes, specify: phone number 1, phone number 2

D. OTHER

Comment:

SHEDDING

Study ID Number ___ ___ ___

Interviewer Number ___ ___

Date of interview (day/month/year) ___ ___ / ___ ___ / ___ ___ ___ ___

Visit (tick one) Week 1 FU Week 2 FU Week 3 FU Other, specify _____

A: MEDICAL HISTORY

1. Has the patient experienced any lower abdominal pain since the last visit?

Yes No

If yes, indicate:

a. Duration ___ ___ days

b. Severity (scale from 1 to 5; 5 being most severe) ___ ___

2. Has the patient experienced any vaginal bleeding since the last visit?

Yes No

If yes, indicate:

a. Duration ___ ___ days

b. Volume

 Stain pants Requires sanitary pad Other, specify

3. Has the patient experienced any vaginal discharge since the last visit?

Yes No

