No dysplasia (NIL)

CIN 1

CIN 2

CIN 3

Invasive carcinoma

Indeterminate/

CIS

Other, specify

10. Was there evidence of cervicitis? F Yes F No Other, specify

11. Who read the biopsy and gave this histology result?

Pathologist Interviewer number ____

12. Comments:

--

CD4 REPORT

Study ID Number

Hope ID Number

Visit (tick one) Randomization/LEEP Visit Month 6FU Month 12FU Month 18FU Month 24FU Other, specify

Patient Age

Interviewer number

1. Date sample was collected in clinic (day/month/year) / /
2. Time sample was collected in clinic
3. Date sample was received in laboratory (day/month/year) / /
4. Time sample was received in laboratory
5. When was the CD4 count run? (day/month/year) / /
6. What was the result of the CD4 count?
7. Who ran the CD4 count and gave this CD4 result? Coptic lab F Other, specify

8. Comments:

FOLLOW-UP FORM

Study ID Number _____ Hope ID Number _____ Interviewer Number _____

Date of interview (day/month/year) _____/_____/_____

Visit (tick one) Month 6 FU Month 12 FU Month 18 FU

Month 24 FU Other, specify _____

A: MEDICAL HISTORY

1. Did you consult a doctor or clinical officer between today and your previous study visit?

- Yes
- No (go to question 2)
- Don't know (go to question 2)
- Refused (go to question 2)

If yes:

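### The Month 6–24 Follow-up form carries none of the symptom questions that the Adverse Events section requires at each visit, so late complications are not elicited in the same way as those in weeks 1–3

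*Combined protocol and SAP*

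**What the plan says.** Category 1 of the Adverse Events section covers occurrences related to the Pap smear, LEEP or cryotherapy. After abdominal pain lasting beyond a few days, it lists the other symptoms and the timing: "vaginal bleeding and/or discharge, fever, or chills will be assessed at each study visit", the trigger being a preceding Pap smear or biopsy. Category 3 adds an open inquiry by staff about new or worsening medical problems since the previous visit.

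Under Study Procedures, treated women "will be followed every 1 week for 3 weeks AFTER the treatment intervention to assess healing" (item 4), and then "will return at 6, 12, 18, and 24 months after treatment is administered" (item 5). Item 5's list for the late visits is a Pap smear, HPV testing from the same swab, blood for CD4 and the Pap Smear questionnaire. It mentions no symptom inquiry and no adverse event form.

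In Appendix B, the Shedding form is for Weeks 1, 2 and 3, with an Other box. It asks questions such as "Has the patient experienced any vaginal bleeding since the last visit", with matching items on lower abdominal pain, discharge and fever, and directs staff to the Adverse Events form. The Follow-up form for Months 6 to 24 opens its medical history with "Did you consult a doctor or clinical officer between today and your previous study visit". It goes on to ARV use, cervical treatment received elsewhere and sexual history.

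Ethics section G lists the severe events of interest, including "severe infection including PID, severe bleeding or cramping and severe cervical stenosis". Among the Study Stopping Criteria is: "The data show a significantly increased risk of serious adverse effects in one of the treatment arms".

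**The concern.** The protocol text and the form used at late visits do not match. The text asks for the same symptoms at every visit, but the form used from Month 6 onward has nowhere to record them. A blank late record cannot then separate a woman who was asked and had no symptoms from one who was never asked. The required-answer checks described under Data Management do not help, because they protect only questions that exist.

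What is at stake is the comparability of safety data over time and between arms. All serious and non-serious adverse events go to the DSMB, which sees data by masked group and may stop for an excess of serious adverse effects in one arm. The QA/QC section also calls for a bi-monthly review of complication rate and type for each procedure. Those reviews would combine checklist-based data from the first three weeks with less structured data from the rest of follow-up. Part of any fall in complications over time could then reflect the method of asking. Staff are not blinded to arm, which makes uniform written questions more valuable.

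**Working it through.** The plan states no figure on this point, so the check sets the forms side by side and counts visits.

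**Does the requirement reach the late visits?** Yes. Its trigger is a preceding Pap smear or biopsy, and every woman at Months 6 to 24 has had one.

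**What does each form capture?**

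| Item | Shedding form (weeks 1–3) | Follow-up form (Months 6–24) | Pap Smear form (Months 6–24) |
|---|---|---|---|
| Abdominal pain | Asked for the interval, with duration and severity | None | Abdominal, uterine and adnexal tenderness that day |
| Bleeding | Asked for the interval | None | Contact bleeding or bloody discharge that day |
| Discharge | Asked for the interval | None | Abnormal discharge that day |
| Fever | Asked for the interval | None | Temperature that day |
| Chills | None | None | None |
| Infection or complication | Procedure-related infection or complication | Consultations only, with sickness as one reason | Diagnoses that day, including PID |
| Hospital admission | No dedicated item | None | None |
| Cervical stenosis | No dedicated item | None | No dedicated item; free text only |
| Prompt for Adverse Events form | Yes | No | No |

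**Count by visit.**
- Scheduled post-treatment visits: 3 (weeks 1, 2, 3) + 4 (Months 6, 12, 18, 24) = 7.
- With structured symptom questions: 3/7 = 43%.
- Without: 4/7 = 57%, which is all of the late visits.

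**Count by calendar time.** Two years is 2 × 52 = 104 weeks, so the checklist covers 3/104 = 2.9%. If a woman who missed her shedding visits returns within six weeks and the form is used then, the figure is at most 6/104 = 5.8%. These percentages describe time under structured questioning. They do not measure risk or events lost.

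**Recall interval.** The gap from week 3 to Month 6 is about 26 − 3 = 23 weeks, and each later gap is about 26 weeks. A bleed, infection or admission that began and resolved within such a gap leaves no sign for a same-day examination to find.

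**What cannot be computed.** The documents give no rate of complications after week 3 and no estimate of how completely an open inquiry captures them. Neither the share of late events missed nor any difference in capture between arms can be derived.

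**The case against.** The strongest reply is that late visits have other safety capture. Category 3 requires an active inquiry with no time limit. Ethics section G has any adverse event recorded when it occurs or at the next visit. The Adverse Events form has boxes for Months 6, 12, 18 and 24 and a column for seriousness. The Pap Smear form records examination signs and a PID diagnosis at each of those visits. Taking the smear passes a brush into the endocervical canal, which gives the examiner a direct chance to notice severe stenosis. The study can also consult Hope Center records. The protocol expects post-procedure cramps, discharge and bleeding to settle within about two weeks, so the checklist covers the main expected period. Statistical Methods plans no test of complications by arm, and the stopping criterion concerns serious effects, which depend least on a checklist of mild symptoms.

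Most of this stands. A reader might infer that late harms go largely uncounted, or come to light only if the woman volunteers them. The required inquiry and the provision for late adverse event forms contradict that.

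It does not close the gap. The open inquiry has no field on the Follow-up form and is absent from the listed late-visit procedures. The Adverse Events form records what has already been elicited and does not itself elicit anything. The examination sees only the day. Inpatient hospitalization is a serious adverse event by the protocol's own definition, yet the late form asks only about consultations, and an admission elsewhere need not appear in Hope Center records.

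**Conclusion.** The mismatch is real and can be verified from the documents. The required symptoms are on a post-treatment checklist at 3 of 7 scheduled visits and at none of the four late ones. Chills is on neither the Shedding nor the Follow-up form, and admission and cervical stenosis have no dedicated item at late visits. The supportable consequence is limited: events that resolve between six-monthly visits may be under-recorded, and late rates are not comparable with those from weeks 1–3.

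Two further inferences should not be drawn:

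- **That about 97% of harms fall outside capture.** The 3-in-104-weeks figure is calendar time, and complications expected from these procedures cluster early.
- **That the loss biases toward no difference between arms.** That would require under-recording to be equal by arm, which is not assured with unblinded staff. Even equal under-recording shrinks a risk difference but need not change a ratio.

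The point is confined to post-treatment follow-up. The Randomization form asks about pain and discharge before treatment, and the Treatment form asks about complications on the day. The conclusion assumes that the forms in Appendix B are those in use and that no separate late-visit symptom checklist exists. It is a low-cost improvement to safety data and does not touch the primary comparison.

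**What to change.** Bring the Follow-up form into line with the Adverse Events section:

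1. Add the Shedding form's questions on pain, bleeding, discharge and fever since the previous visit.
2. Add yes/no items for chills, hospital admission and cervical stenosis. Add chills to the Shedding form too, so that both match the text.
3. Carry over the instruction to complete the Adverse Events form.
4. In the DSMB report, tabulate complications by arm separately for weeks 0–3 and for later follow-up, so that periods with different ascertainment are not pooled.

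This adds about seven items (four copied and three new) to an existing form at existing visits and changes no clinical management. The cost is a few minutes per visit. Women followed before the change would have no structured late data, so the date of the change should be recorded and the later-period table should show how many women were seen under each version of the form.

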Based on the high incidence of cervical cancer in Kenya and building upon our programmatic and research work in cervical cancer screening among HIV-positive women, we propose to study the effect of LEEP versus cryotherapy on the recurrence of cervical intraepithelial neoplasia and the shedding of HIV-1 from the cervix. Our hypothesis is that compared to cryotherapy, LEEP is significantly more likely to prevent recurrence of cervical lesions over 2 years of follow-up and less likely to shed HIV-1 from the cervix over 6-weeks of follow-up. This evaluation will inform PEPFAR policies on the best method to treat pre-cancerous lesions in HIV-positive women and elucidate the importance of cervical treatment interventions according to immune status and antiretroviral therapy. Such information is directly relevant to the care of HIV-positive women in Kenya and other resource-limited countries which are significantly impacted by cervical cancer.

Timeline and Dissemination

The duration of the evaluation activity is approximately 6 years from the beginning of the funding cycle. It is estimated that it will take at least 3 years to screen at least 2,400 women and randomize approximately 400 women with high grade intraepithelial lesions to LEEP vs. cryotherapy. These randomized participants will be followed for 2 years after screening or randomization. Including preparation and analysis, it is expected that it will take approximately 6 years to complete this study.

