Results of the study will be shared directly with the USG/GOK technical teams through annual reports and regular e-mail contact with designated contacts at the CDC in Atlanta and Nairobi. Reports will include analysis from regular DSMB meetings. After initiation of the study, we will confer with the CDC on whom to report to in Kenya and Atlanta. At that time, we will also determine how frequently the USG/GOK technical teams would like to be appraised of the study and its results. At a minimum, we will seek to be in phone and/or e-mail contact with USG contacts quarterly to ensure that the study and its data is relevant to USG technical working groups and policies established around cervical cancer screening in PEPFAR-supported clinics. Dissemination of study findings will also occur through public presentations and publication in internationally recognized journals. CDC and USG staff/agents will not participate in the study as co-investigators or study collaborators. They will not participate directly in the study development, analysis, or manuscript preparation.

Cervical Screening Organogram

Personnel

Study Coordinator

- Manage directly the Study Monitor, Data Manager, Study Doctor, Administrator, and Lab technologist around aspects of the PHE cervical treatment study and R01 resistance study
- Monitor the progress of research activities and ensure the smooth and efficient day-to-day operation of research and data collection activities
- Initiate and coordinate activities that improve the conduct and performance of the study
- Conduct weekly clinic meetings that are led by Study Doctor with study staff
- Conduct weekly data meetings that are led by the Data Manager to ensure data is collected in a timely fashion, is cleaned, and clearly analyzed
- Conduct and lead weekly study-related administrative meetings
- Direct and be responsible for the study budget and petty cash that is managed by the administrator
- Act as the primary administrative point of contact for research staff and as the principle operational liaison for Coptic administration and regulatory bodies
- Analyze recruitment rates, determine if rates match expectations, and implement plans that will promote recruitment
- Analyze retention rates and implement plans that will promote retention
- Supervise and coordinate the provision of support services to investigators
- Prepare periodic and ad hoc reports as required by investigators, funding agency, and/or regulatory bodies

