Outcome of Adverse Event:

All AEs must have their outcome assessed as either “resolved without sequelae”, “resolved with sequelae”, “ongoing”, “death”, “unknown.” The study clinician is responsible for assessing outcomes and recording them on the appropriate CRF.

Definition of Serious Adverse Event (SAE)

An SAE is defined as an AE that meets one of the following conditions:

- Death during the period of protocol defined surveillance
- Life-threatening event (defined as a subject at immediate risk of death at the time of the event)
- An event requiring inpatient hospitalization or prolongation of existing hospitalization during the period of protocol defined surveillance
- Results in congenital anomaly or birth defect
- Results in a persistent or significant disability/incapacity
- Any other important medical event that may not result in death, be life threatening, or require hospitalization, may be considered a serious adverse experience when, based

upon appropriate medical judgment, the event may jeopardize the subject and may require medical or surgical intervention to prevent one of the outcomes listed above.

Data Safety and Monitoring Plan

Introduction

The data safety and monitoring board (DSMB) will act in advisory capacity to the CDC, UW, KNH, UoN, Coptic Hospital, and IARC – WHO to monitor patient safety and evaluate treatment interventions for this study. [name] (UW) will be Chairman of the DSMB.

After its first meeting around study initiation, the DSMB will be responsible for reviewing interim safety and efficacy analyses at five time points during the 3 year study period. These meetings and reviews of interim analyses are expected to occur at approximately 4, 9, 15, 21, and 27 months after study initiation.

- 1) The first meeting will take place when 100 participants have received the study intervention, and this is expected to occur around 4 months after study initiation.
- 2) The second meeting will take place when 75 participants have received Month 6 Pap smear results, and this is expected to occur around 9 months after study initiation.
- 3) Thereafter, DSMB meetings and interim analyses will occur every 6 months after this second meeting or approximately at 15, 21, and 27 months after study initiation.

The DSMB will have the following responsibilities:

1. Review the research protocol and plans for data safety and monitoring;

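### The listed DSMB reviews stop at about month 27 of a 3-year study, but the protocol's own timeline puts the last 24-month visit at month 60 or later

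*Combined protocol and SAP*

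**What the plan says.** All references are to the combined protocol and SAP.

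The Introduction of the Data Safety and Monitoring Plan makes the DSMB responsible for "reviewing interim safety and efficacy analyses at five time points during the 3 year study period", and adds: "These meetings and reviews of interim analyses are expected to occur at approximately 4, 9, 15, 21, and 27 months after study initiation". The first review takes place "when 100 participants have received the study intervention, and this is expected to occur around 4 months after study initiation", and the second "when 75 participants have received Month 6 Pap smear results, and this is expected to occur around 9 months after study initiation". After that, "DSMB meetings and interim analyses will occur every 6 months after this second meeting or approximately at 15, 21, and 27 months". Interim Efficacy Analyses repeats months 9, 15, 21 and 27 for the efficacy comparisons. The Meetings paragraph says that the DSMB meets on the schedule already outlined.

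Timeline and Dissemination gives a different duration: "It is estimated that it will take at least 3 years to screen at least 2,400 women and randomize approximately 400 women". It then gives 2 years of follow-up for randomised women and, with preparation and analysis, "it is expected that it will take approximately 6 years to complete this study". Study Procedures, item 5, places outcome visits at 6, 12, 18 and 24 months after treatment.

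Two other places rely on a continuing series of meetings. On reports to the technical teams, Timeline and Dissemination says "Reports will include analysis from regular DSMB meetings". Reporting of Adverse Events routes all serious and non-serious events to the DSMB at its regular meetings.

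**The concern.** The two sections describe trials of different length and speed. If staff follow the DSMB section as written, the last scheduled review comes while most women have yet to reach 24 months, and under uniform accrual before randomisation has finished.

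Scheduled independent review of accumulating data by arm is what would be lost. The DSMB is charged with assessing retention, and the stopping criteria name excess dropout and missing data; much of the two-year retention picture forms after review 5. Under Confidentiality, only voting DSMB members normally see interim outcome data by group. A difference between arms may therefore not prompt anyone outside the board to ask for a meeting.

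**Working it through.** **Inputs.** 400 women (Statistical Methods); at least 36 months to randomise and 24 months of follow-up (Timeline and Dissemination); milestones of 100 treated at about month 4 and 75 Month-6 results at about month 9, then 6-month spacing (DSMB plan); 20% loss (Statistical Methods).

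**The plan's own dates.** 9 + 6 = 15, 15 + 6 = 21, 21 + 6 = 27. The listed months reproduce, and review 5 = review 2 + 18 months.

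**Duration.** 36 + 24 = month 60 at the earliest, against 36 months in the DSMB plan.

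**Pace.** DSMB plan: 100/4 = 25 per month. As a check, 75 Month-6 results at month 9 means 75 treated by month 9 − 6 = 3, and 75/3 = 25. Timeline: 400/36 = 11.1 per month at most, on average. Ratio: 25/11.1 = 2.25. At 11.1 per month, 11.1 × 4 = 44 women are treated by month 4, and the 100th at 100/11.1 = month 9.

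**24-month results at review 5.** These need treatment by review 5 − 24 = review 2 + 18 − 24 = review 2 − 6. That is the same cut-off as for the 75 Month-6 results that trigger review 2. So the figure is about 75 of 400 (75/400 = 18.75%), whenever review 2 occurs. About 400 − 75 = 325 of the 24-month visits follow; with 20% loss, at least 320 − 75 = 245.

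**Time from review 5 to the last 24-month visit:**

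- Fixed dates: 60 − 27 = 33 months, a minimum because accrual takes at least 36 months.
- Count triggers, uniform accrual from month 0 to 36: the 75th woman is treated at 75/11.1 = 6.75; review 2 at 12.75; review 5 at 30.75; 60 − 30.75 = 29 months.
- The same with first treatment at month 1.75 (the 6-8-week visit) and an assumed 0.5 month for results: rate 400/34.25 = 11.68; review 5 at 1.75 + 6.42 + 6.5 + 18 = 32.67; 60 − 32.67 = 27 months.
- Count triggers with an assumed 12-month linear ramp-up, ending at month 36: steady rate 400/(6 + 24) = 13.33; 13.33t²/24 = 75 gives t = 11.62; review 5 at 11.62 + 24 = 35.62; 60 − 35.62 = 24 months.
- Count triggers, uniform accrual over an assumed 48 months: rate 8.33; the 75th woman at month 9; review 5 at 9 + 24 = 33; 72 − 33 = 39 months.
- The DSMB plan's own 25 per month: accrual ends at 400/25 = 16; last visit at 40; 40 − 27 = 13 months.

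**Earlier results at review 5** (uniform accrual, count triggers, month 30.75): 6-month 11.11 × 24.75 = 275; 12-month 11.11 × 18.75 = 208; 18-month 11.11 × 12.75 = 142.

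**Women still to be randomised at review 5:** 400 − 11.11 × 30.75 = 58 under uniform accrual; about 13.33 × (36 − 35.62) = 5 with the ramp-up.

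**The case against.** The best defence is that the six-monthly rule states no end. The months are only expected and approximate, and the count of five is tied to the same 3-year period that cannot be right. On that reading the dates are out of date but the series continues. This is possible, but the text does not say it: the count of five, the listed months, their repetition under Interim Efficacy Analyses and the cross-reference under Meetings all close the list. At best the end of the series is unclear, and that alone warrants a sentence.

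Second, the DSMB section is coherent on its own terms. If first treatment is at month 1.75, its first milestone implies 100/2.25 = 44.4 per month and a last visit at 1.75 + 9 + 24 = month 34.75, inside 3 years. That pace is four times the Timeline's average, so the conflict between sections remains.

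Third, the figure of 75 is not a strict ceiling. A woman who missed month 6 but attended month 24 would add to it. Normal and ASCUS results are disclosed only at the next scheduled visit, so a literal reading of results received could delay review 2 by up to about 6 months. At the uniform pace that would raise the count to at most 75 + 6 × 11.1 = 142 and cut the 29 months to about 23. The plan's month-9 expectation favours the ordinary reading, hence about 75.

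Fourth, the 24-month count is only part of the information: review 5 would hold many more 6- to 18-month results. Treatment is a single procedure, and most expected procedural effects are described as lasting days to weeks. Requested and emergency meetings are allowed at any time, SAEs go to the IRBs and the sponsor, and the study team reviews complications bi-monthly. All of this stands and limits the consequence. None of it is a scheduled independent review by arm.

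**Conclusion.** The inconsistency is firm and needs no assumption: a 3-year study with reviews ending at about month 27 cannot be squared with at least 36 months of randomisation plus 24 of follow-up. It is also firm that review 5, as defined, sees about 75 of 400 women at 24 months.

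The length of the unreviewed period depends on how the dates and accrual are read: at least about 33 months on the fixed dates; about 29 with count triggers and uniform 36-month accrual; shorter with a slow start, longer if accrual exceeds 36 months; about 13 at 25 per month. A reader might take 33 months as the upper limit, or read a precise lower limit into a slow-start scenario. The documents support neither: 36 months of accrual is itself a minimum, and no ramp-up is described anywhere.

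A reader might also infer that type I error is inflated or that early stopping becomes more or less likely. Neither follows. Interim Efficacy Analyses specifies Lan-DeMets spending for looks at other times, and the documents define no information scale from which a stopping probability could be computed. Nor does the trial lack safety oversight. The gap is in scheduled independent review.

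**What to change.** Reconcile the DSMB plan's Introduction and Interim Efficacy Analyses with Timeline and Dissemination:

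- Replace the 3-year period and the expected months with ones that match planned accrual. Under uniform 36-month accrual, review 1 would be expected at about month 9 and review 2 at about month 13.
- State that the counts (100 treated; 75 with Month-6 results) trigger reviews 1 and 2, and that the months are forecasts only.
- State that scheduled DSMB reviews then continue every 6 months until the last participant's 24-month visit.
- State that the added reviews cover safety and study conduct only, unless an efficacy look is taken under the Lan-DeMets O'Brien-Fleming spending already specified.

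The cost is a wording change plus about four or five extra teleconferences (29/6 = 4.8; 33/6 = 5.5, so five fall before month 60), and more if accrual runs beyond 36 months. Reviews limited to safety and conduct spend no alpha.
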